## 5.3 Evaluation of adverse events

The possible association of adverse events and surgical intervention was assessed by the following criteria:

I.Definitely unrelated: adverse events were not associated with the use of surgical intervention. E. g.: No robotic surgery was performed.

II.Probably unrelated: There is no evidence of a causal relationship between the occurrence and surgical intervention. The occurrence of adverse events is more likely to be related to other factors, such as surgical intervention or concomitant diseases. However, the correlation between the two factors cannot be excluded.

III.Possible related: The occurrence of adverse events and surgical intervention have a reasonable chronological order, and the occurrence of adverse events may be caused by surgical intervention. It cannot be excluded from other factors, such as surgical intervention or concomitant diseases. No withdrawal or unclear.

IV.Affirmation: The type of adverse event has been identified as the type of response to surgical intervention and cannot be explained by other reasons (e. g., surgical intervention and concomitant diseases). The timing of the event strongly

suggests causality.

V.Unable to assess: Lack of sufficient information to judge the causality of the event and surgical intervention. The investigator may change the causality assessment she / he does based on the follow-up information and modify the corresponding AE / SAE report.

## 6.Data collection and management

### 6.1 Data collection method

Data collection was conducted by Excel 2010 combining double data entry and CRF form. The specific requirements and implementation details are as follows:

(1) For all patients who have completed informed consent and screened qualified, the medical record and CRF form should be written carefully and detailed. All items should be filled in without empty items as far as possible.

(2) The original laboratory sheet should be complete and attached to the original case. All the original laboratory sheet, CT, MRI, colonoscopy, ultrasound, etc. should be signed and dated by physicians and researchers participating in the clinical study. and the data recorded by CRF should be checked with the medical record and the original test report.

(3) The original date (hospitalization medical record) shall be taken as the original record, any correction can only be underlined, the modified data shall be annotated, the reasons shall be explained, and signed and dated by the doctors and researchers participating in the clinical study, and the original record shall not be erased or covered.

(4) The data significantly high or beyond the clinically acceptable range shall be verified, and the physicians participating in the clinical study shall make necessary instructions.

### 6.2 Data management

(1) For all patients who have completed informed consent and screened qualified, the medical record and CRF form should be written carefully and detailed. All items should be filled out (see filling instructions).

(2) The original laboratory sheet shall be complete and attached to the original

cases. All the original laboratory sheet, CT, ultrasound and other cases shall be signed and dated by the doctors and researchers participating in the clinical study. The data recorded by CRF shall be checked with the medical record and the original test report.

(3) The original date (hospitalization medical record) shall be taken as the original record, any correction can only be underlined, the modified data shall be annotated, and the reasons shall be explained, and signed and dated by the doctors and researchers participating in the clinical study, and the original record shall not be erased or covered.

(4) The data significantly high or beyond the clinically acceptable range shall be verified, and the physicians participating in the clinical study shall make necessary instructions.

(5) The records of relevant intraoperative indicators must be provided by the surgeon and accurately filled in the CRF form within 6 hours after the operation.

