## Scenario summary

research topic	Application of Single-Port Robot-Assisted Breast-Conserving Surgery via Axillary Approach for Breast Cancer.
Main purpose of the study	
1. To evaluate the efficacy of single-port robots in breast cancer breast conserving surgery. Including differences in operative time and intraoperative number of lymph nodes detected.
 
2. To evaluate surgical safety: the incidence of surgical transfer and the incidence of postoperative complications.

Secondary purpose of the study	Pain and cosmetic scores of patients after breast conserving surgery under a single port robotic approach.
research design	
 Randomized controlled trial
 
 non-randomized controlled study
 
 Single-arm study
 
 Other
 
 Single-center study    multicenter study
 
Whether blind:  yes  no

subject investigated	Patients undergoing breast-conserving surgery for breast cancer.
intervention study	Single-port Robot-assisted breast-conserving surgery for breast cancer.
endpoint criteria	Success rate of breast conservation surgery under single-port robotic approach
sample capacity	Total number of cases: 100; 20 in the test group; 80 in the control group

statistical analysis	Double data entry was carried out using Excel 2010, and data analysis was performed with SPSS 25.0. The normality of continuous variables and homogeneity of variance were examined by Kolmogorov-Smirnov test and analysis of variance test respectively. For continuous variables that conformed to normal distribution and had homogeneity of variance, the independent-samples t-test was adopted. For continuous variables that did not conform to normal distribution, the Mann Whitney U test was used. For categorical variables and count data, Fisher's exact test and Pearson chi square test were employed.
Study cycle	November 2024-December 2025

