## 3. Research Design

### 3.1 Overall Study Design

-Enrollment: Subjects who meet the inclusion criteria enter the study process, including SPr-breast conserving surgery or Traditional-breast conserving surgery. The choice of the two surgical methods is based on the patients economic situation and the availability of equipment.

-Preoperative hospitalization: Collect patient disease information (including mammography, breast B ultrasound, breast enhanced MRI, etc.).

-The day of operation: Record the operation time, intraoperative bleeding volume, intraoperative complications, intraoperative adverse events, etc.

-Postoperative hospitalization: Record postoperative complications (postoperative bleeding, flap or nipple areola complex necrosis, subcutaneous emphysema, infection, capsular spasm, postoperative shoulder pain and discomfort, etc.), postoperative pain score, and postoperative pathological biopsy.

-Postoperative hospital stay: Calculated based on the number of days from surgery to discharge.

[figure not shown]
-28 days after surgery: To understand the complication rate and mortality rate within 28 days after surgery.

-90 days after surgery: To understand the complication rate and mortality rate within 90 days after surgery.

-Disease-free survival at 3 years after surgery (recurrence was defined as surgical area and distant metastasis by the time from surgery to last follow-up or date of recurrence and metastasis).

-3 year overall survival (from time from surgery to last follow-up or death).

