## 3.4 Study grouping and methods

### 3.4.1 Study groups and interventions

The surgical method is based on the advice of the physician, mainly on the own choice of patients and the availability of equipment. After rigorous preoperative evaluation, patients who met the inclusion criteria were prepared for preoperative preparation (including preoperative antibiotics, etc.). The observation group was the SPr-breast conserving surgery group and the control group was the tradition-breast conserving surgery group.

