## 7.Quality control

(1) Conduct comprehensive training for all participating personnel (including researchers, research nurses, data entry staff, etc.). For example, for the researcher, the inclusion criteria, exclusion criteria, and the specific operation procedures of the intervention measures should be explained in detail.

(2) The personnel participating in the clinical trial should have the corresponding professional expertise, qualification and scientific research ability, and must carefully study and discuss the clinical research plan and trial manual, and be determined after the qualification examination, and the personnel are relatively fixed. Archives management, use of drugs or devices, and correction of relevant testing instruments shall be managed by qualified personnel. Through clinical trial training to make research personnel for clinical trial scheme and its index specific connotation fully understand and understanding, for the description of conscious symptoms should be objective, do not induce or prompt: for the objective indicators shall be specified by the time, place and method of inspection, should pay attention to observe adverse reactions, and tracking.

(3) In order to eliminate the skill differences of surgeons and the potential impact

of surgeon learning curve on the results, only single-port or multi-channel robotic surgical patients with two senior physicians in our department were selected for comparative analysis. Both surgeons have completed more than 30 cases of robotic surgery and have passed the learning curve of robotic surgery.

(4) Standardized implementation of interventions

Establish the intervention implementation record system, detailed record of the time of each intervention, executor, patient response and other information. This traces the implementation of the intervention to facilitate problem detection and quality control.

(5) Normalization of follow-up

Develop a perfect follow-up plan, and clarify the follow-up time point, follow-up content and follow-up method. Follow-up personnel were trained to ensure accurate follow-up data collection.

A follow-up reminder system was established to remind patients to follow up on time through SMS and telephone calls, so as to improve the follow-up rate and ensure the integrity of the study data.

(6) Regular internal quality inspection:

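### The surgeon, who cannot be blinded, is the required provider of operation time and blood loss, and no stated safeguard for these two items is independent of the surgeon (minor; cheap to improve)

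*SAP*

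**What the plan says.** Section 6.2(5) names one provider and one deadline. The records of the relevant "intraoperative indicators must be provided by the surgeon and accurately filled in the CRF form within 6 hours after the operation". The item does not list the indicators. Section 3.1 gives the tasks for the day of operation: "Record the operation time, intraoperative bleeding volume, intraoperative complications, intraoperative adverse events, etc". In the section 3.6 schedule, operation time and intraoperative bleeding are the only surgery-related indicators marked for that day.

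The Scenario summary ticks non-randomized and not blinded. It explains the efficacy part of the main purpose with the words "Including differences in operative time and intraoperative number of lymph nodes detected". The safety part reads "To evaluate surgical safety: the incidence of surgical transfer and the incidence of postoperative complications".

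On allocation, section 3.4.1 says "The surgical method is based on the advice of the physician, mainly on the own choice of patients and the availability of equipment". On operators, section 7(3) restricts the robotic cases to patients of "two senior physicians in our department were selected for comparative analysis".

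On sources, section 6.2(3) says "The original date (hospitalization medical record) shall be taken as the original record", and 6.2(2) has the CRF checked against the medical record and the original test report.

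**The concern.** The surgeon always knows which technique was used and has had a part in advising it. If the same person is also the required provider of the time and blood-loss records, any tendency to report one technique more kindly enters the comparison directly. Both quantities leave room for judgement. The length of an operation depends on when the clock starts and stops, and blood loss is often an estimate. Robot set-up exists in one arm only, so an inconsistent way of counting it would not cancel between arms.

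At stake is the comparison of operative time, which the study names as a main purpose, and the supporting comparison of bleeding. Since the surgeon cannot be blinded, the part that can be corrected is the source of the data.

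**Working it through.** The SAP gives no figure to reproduce, so the check is a reading of the relevant sections together.

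**Step 1: does the rule reach comparative outcomes?** Section 6.2(5) does not itemise its indicators. Operation time and bleeding appear both in section 3.1 and in the section 3.6 schedule for the operation day, so including them is well supported. Including intraoperative complications rests on section 3.1 alone. The safety part of the main purpose names conversion and postoperative complications, not intraoperative ones. The point is therefore limited to time and bleeding.

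**Step 2: is any stated safeguard independent of the surgeon for these two items?**

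- CRF check against the medical record (6.1(2), 6.2(2)): this is a real check on transcription. The SAP does not say whether the operative entries in that record come from the surgeon or from someone else.
- Intervention log (7(4)): it holds the time and executor of each intervention. It names no recorder and is not linked to the outcome data.
- Internal quality inspection (7(6)): it covers data collection and entry, but the research team does it.
- DSMB review (7(9)): it covers clinical and safety endpoint events. It is not described as a source for the length of an operation or the volume of blood lost.
- Core laboratories (7(10), 7(11)): two experts judge independently and a third decides, but only for imaging and pathology.

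None is stated to supply time or bleeding independently of the surgeon.

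**Step 3: how would an error act?** Write e_R and e_T for the mean reporting error in the robotic and traditional arms. Then

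observed difference = true difference + (e_R − e_T).

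Equal errors cancel and unequal errors do not. The SAP gives nothing from which e_R or e_T could be estimated, so the size and even the presence of a net bias are unknown.

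**Step 4: what is not touched?** The primary endpoint is margin status (3.8, 4.4), and pathology goes to the core laboratory. The lymph node count is also outside this point if it is taken from pathology. The secondary endpoints in 3.8.2 are pain and cosmetic scores. Time and bleeding appear in neither endpoint list (3.8, 4.4); operative time enters through the main purpose in the Scenario summary.

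**The case against.** The strongest reply is that section 6.2(5) concerns handing over records. Its subject is the records of the indicators, so it says who delivers them and by when. It does not say that the surgeon times the operation or estimates the blood loss. This stands, and it limits the point to exposure to bias. The rule still makes the surgeon the required provider, with no other origin stated.

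A second reply is that start and stop points, measurement methods and source lists usually sit in a protocol or manual. Section 6.2(1) refers to filling instructions and section 7(2) to a trial manual, neither of which is shown. Section 7(2) also asks that time, place and method be specified for objective indicators. This stands too: the lack of a definition here is not a fault in itself. The point rests on the provider that the SAP does state.

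A reader might infer more than the text supports:

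- **That 6.2(3) and 6.2(5) contradict each other.** They do not. Item (3) fixes the original record and how it is corrected, item (5) fixes who supplies intraoperative records and when, and item (2) joins them through the CRF check. One entry can satisfy all three.
- **That values are recalled hours later.** Six hours is a deadline. Values may be noted during surgery.
- **That the operators themselves lead development of the technique.** Section 1 states that ambition for the hospital team, not for each surgeon.
- **That the bias is 10 to 30 minutes.** If s minutes of set-up were counted in a fraction p of robotic cases, the robotic mean would move by p × s. For an assumed s of 10 to 30 minutes, that is anywhere from 0 (p = 0) to 10 to 30 minutes (p = 1). But s is not in the document, and the shift comes from an undefined interval. A nurse without a definition would face the same ambiguity.
- **That 5 percentage points measures bias.** One event among 20 robotic patients is 1/20 = 5 points. That is the weight of any single event and is not evidence of under-reporting.

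**Conclusion.** The point holds as a cheap improvement of minor severity. In an open-label, non-randomized study, the SAP makes the surgeon the required provider of operation time and bleeding, and states no safeguard for them that is independent of the surgeon. The comparison of these two outcomes is exposed to reporting bias of unknown size.

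This rests on two readings: that the surgeon in 6.2(5) is the operating surgeon, which is the only natural one, and that the relevant indicators include time and bleeding, as 3.1 and 3.6 show. It does not rest on a conflict within section 6.2, and it gives no reason to doubt the primary endpoint.

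**What to change.** Reword section 6.2(5) to say that:

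- operation time and bleeding are taken from the anaesthesia or theatre nursing record made during the operation;
- operation time runs from first incision to last stitch in both arms;
- robot set-up time is recorded as a separate item;
- the surgeon supplies only technical items, such as the reason for conversion.

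The 6-hour deadline can stay, and no separate data-entry person is needed. If the trial manual or filling instructions already fix the source and interval, 6.2(5) should be brought into line and refer to them.

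The change concerns measurement only. It costs one edit and slightly more transcription, and the robotic figures may look less favourable. It assumes that theatre records of this kind are kept routinely at the centre, which the SAP does not state and the sponsor should confirm.

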## 7.Quality control

(1) Conduct comprehensive training for all participating personnel (including researchers, research nurses, data entry staff, etc.). For example, for the researcher, the inclusion criteria, exclusion criteria, and the specific operation procedures of the intervention measures should be explained in detail.

(2) The personnel participating in the clinical trial should have the corresponding professional expertise, qualification and scientific research ability, and must carefully study and discuss the clinical research plan and trial manual, and be determined after the qualification examination, and the personnel are relatively fixed. Archives management, use of drugs or devices, and correction of relevant testing instruments shall be managed by qualified personnel. Through clinical trial training to make research personnel for clinical trial scheme and its index specific connotation fully understand and understanding, for the description of conscious symptoms should be objective, do not induce or prompt: for the objective indicators shall be specified by the time, place and method of inspection, should pay attention to observe adverse reactions, and tracking.

(3) In order to eliminate the skill differences of surgeons and the potential impact

of surgeon learning curve on the results, only single-port or multi-channel robotic surgical patients with two senior physicians in our department were selected for comparative analysis. Both surgeons have completed more than 30 cases of robotic surgery and have passed the learning curve of robotic surgery.

(4) Standardized implementation of interventions

Establish the intervention implementation record system, detailed record of the time of each intervention, executor, patient response and other information. This traces the implementation of the intervention to facilitate problem detection and quality control.

(5) Normalization of follow-up

Develop a perfect follow-up plan, and clarify the follow-up time point, follow-up content and follow-up method. Follow-up personnel were trained to ensure accurate follow-up data collection.

A follow-up reminder system was established to remind patients to follow up on time through SMS and telephone calls, so as to improve the follow-up rate and ensure the integrity of the study data.

(6) Regular internal quality inspection:

The research team periodically (checks the quality of each part of the study, monthly or quarterly). The examination includes the enrollment of research subjects, the implementation of intervention measures, data collection and entry, etc. Problems are found through internal examination, such as missing follow-up data of some patients, and timely analyze the causes and take remedial measures.

Establish a quality inspection report system, form a written report on the results of each quality inspection, inform the research team members, let everyone understand the quality status of the research, and make improvement plans for the existing problems.

(7) Establish a multi-center coordination committee

The multi-center trial coordination committee has the head of each clinical trial unit and the main research coordination committee, which is responsible for the implementation of the whole trial and the study and resolution of issues related to the

trial.

(8) Data and safety monitoring Committee

The Data and Safety Monitoring Committee (DSMB) was established during the implementation phase. The DSMB member is composed of experienced gastrointestinal surgeons and statisticians who are not involved in the execution of the clinical trial. The DSMB is formed by the DSMB Chairman, working under the DSMB Charter, to report the specific outcome measures to the DSMB Chairman under strict confidentiality.

(9) All clinical and safety endpoint events were reviewed in detail by the DSMB.

(10) Image core laboratory

The imaging core imaging Laboratory has three professors as experts. Two experts independently evaluate all the imaging data of the patient, and the third expert will make the final decision in the case of inconsistent conclusions. Imaging data for all patients will be uploaded via storage media and web and evaluated by the Imaging Core Laboratory. The imaging Core laboratory evaluation includes:

In addition, imaging interpretation before patient enrollment was evaluated by at least two gastrointestinal surgeons at each subcenter, and none of the evaluators were involved in the trial execution.

(11) Pathology core laboratory

The pathology core laboratory has three professors as experts, two of the experts will independently evaluate all the pathology data of the patient, and the third expert will make the final decision in the case of inconsistent conclusions. Pathology data of all patients will be uploaded via storage media and web and evaluated by the Pathology Core Laboratory. Pathology core laboratory evaluation includes:

In addition, patient pathology interpretation before enrollment was evaluated by at least two pathologists at each subcenter, and none of the evaluators were involved in the trial execution.

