shows that Jingfeng ®SP1000 is the first single-port surgical robot to enter the registered clinical trial in China. Jingfeng Medical ® has cooperated with top hospitals and top experts in China to carry out in-depth clinical research and trial of all departments of single-port surgical robot. At present, Jingfeng ®SP1000 has been approved for gynecological indications, and completed registered clinical trials in urology, general surgery, thoracic surgery and other fields, successfully carried out more than 200 clinical operations, demonstrating a wide range of adaptability and excellent performance, bringing new value to scientific research and clinical fields. In addition, professor [name]'s team[29-31]. For the first time, the domestic Jingfeng ®EDGE SP1000 surgical system was used to successfully simulate the key steps of thyroid surgery in the oral thyroid surgery simulator, and realized the high-definition vision and high stability of single-arm robot surgical system, and its smart arm technology, hidden sleeve function and zero pressure anchor point technology are more conducive to ensure the operation safety, this successful practice provides a solid foundation and rich experience for single-port robot breast surgery and related clinical research. However, the safety and effectiveness of the procedure have not been fully verified, and whether the single-port robotic transaxillary breast cancer surgery is more advantageous than the multi-channel operating system (Xi and Si) is not reported. Therefore, this study aims to fill this gap and compare the efficacy and safety of open breast cancer surgery and single-port robot in transaxillary breast cancer surgery through a prospective, single-center phase II clinical cohort study, so as to provide scientific basis for clinical practice and promote the development of minimally invasive breast cancer surgery technology. To provide a theoretical and practical basis for the future application of EDGE SP1000 surgical system in breast cancer surgery. In addition, on this basis, we will systematically establish the technical system and standard for single-port robot breast cancer surgery in our hospital, and lead the formulation of domestic single-port robot-assisted breast cancer surgery standard, which is this the clinical promotion and application of surgery to lay a solid foundation

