#### 4.2 Statistical analysis of the population

This study, conducted only in the Army Characteristic Medical Center, is a single-center, prospective clinical cohort study designed to evaluate the safety and efficacy of single-port robots in breast cancer surgery by comparison with the traditional breast-conserving surgery group. During the trial, the clinical data will be

reviewed centrally to ensure uniform quality.

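### Section 7(3) limits the comparative analysis to robotic patients, which contradicts the single-port versus traditional comparison, and it sets no surgeon rule for the traditional arm

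*SAP*

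**What the plan says.** Section 7 (Quality control), item (3), gives its purpose as "In order to eliminate the skill differences of surgeons and the potential impact" of the learning curve, and then sets the rule: "only single-port or multi-channel robotic surgical patients with two senior physicians in our department were selected for comparative analysis". It adds an experience criterion: "Both surgeons have completed more than 30 cases of robotic surgery and have passed the learning curve of robotic surgery". Neither sentence mentions traditional surgery.

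The design sections define the groups differently. Section 3.1 lists the enrolled procedures as "including SPr-breast conserving surgery or Traditional-breast conserving surgery". Section 3.4.1 says: "The observation group was the SPr-breast conserving surgery group and the control group was the tradition-breast conserving surgery group". Section 3.5 describes the same two interventions. Section 1 gives the aim as to "compare the efficacy and safety of open breast cancer surgery and single-port robot in transaxillary breast cancer surgery". Section 4.1 sizes the study as 20 single-port patients against 60 traditional ones (the summary says 80). Section 4.2 says the evaluation is made "by comparison with the traditional breast-conserving surgery group".

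Item (4) of Section 7 requires a log of each intervention that includes who carried it out. Section 4.3 plans t-tests, Mann-Whitney tests, chi-square tests and exact tests, and no adjusted analysis.

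**The concern.** Item 7(3) is phrased as a selection rule for the comparison. It uses the word only, names the eligible patients by type of robotic operation, and attaches the selection to the comparative analysis. The study's control group does not satisfy it, and a group outside the design does. An analyst who followed Section 3.4.1 and one who followed Section 7(3) would build different datasets. Because the SAP does not say which passage governs, the choice could be made after the data are seen.

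There is a second difficulty even if the literal reading is set aside. The rule exists to stop surgeon skill from distorting the comparison, but its restriction and its experience criterion concern robotic cases only. A safeguard applied to one side of a comparison does not secure balance between the sides. Operating time, bleeding, margin status and complications may all depend on who operates. The groups are formed by patient choice, means, physician advice and equipment availability, so randomisation gives no protection either.

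**Working it through.** The SAP states no error rate, power or effect size on this point, so there is no figure to reproduce. The check is a comparison of passages and a head count.

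**Step 1. Who is to be compared?**

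| Place in the SAP | Groups named |
|---|---|
| Section 1, aim | Single-port robot and open surgery |
| Section 3.1 | Single-port or traditional |
| Section 3.4.1 | Single-port (observation) and traditional (control) |
| Section 3.5 | Single-port and traditional |
| Section 4.1 | 20 single-port and 60 traditional |
| Section 4.2 | Single-port and traditional |
| Section 7(3) | Single-port or multi-channel robotic, two senior physicians |

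Six places agree and Section 7(3) stands alone.

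**Step 2. Head count if 7(3) is applied as written.**

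| Group | Planned | Admitted by 7(3) |
|---|---|---|
| Single-port robotic | 20 | at most 20 |
| Traditional | 80 (summary) or 60 (Section 4.1) | 0 |
| Multi-channel robotic | none planned | eligible, but no arm or size defined |

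The planned 20 versus 80 (or 20 versus 60) becomes 20 versus 0 among the planned groups. The chi-square or exact test in Section 4.3 then has no planned comparator. The difference between 80 and 60 is a separate matter and does not affect this result.

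**Step 3. Does anything else in the SAP settle it?** Section 4.2 is headed as the analysis-population section and names the traditional group, but it defines no analysis set and does not refer to 7(3). Multi-arm robots appear elsewhere as background (Section 1) and as the department's earlier experience (Sections 4.5 and 8.1). Section 1 does note that single-port surgery has not been compared with the multi-channel systems, and it says the study will fill this gap, but it then names open surgery as the comparator.

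**Step 4. The lenient reading.** Suppose 7(3) was meant only to limit which surgeons' robotic cases count.

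- Single-port arm: two senior surgeons, each with more than 30 robotic cases.
- Traditional arm: no number of surgeons, no seniority and no experience criterion stated.
- Analysis: unadjusted tests only. The operator is recorded under 7(4), but no planned analysis uses the record.

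Imbalance by surgeon is therefore possible. Its size cannot be derived, because the SAP gives no caseload by surgeon and does not say who performs the traditional operations.

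**The case against.** The strongest reply is that nobody would drop the whole control group on the strength of this sentence. It sits under quality control, while Section 4 names the traditional group as comparator. Section 7 also contains other material that does not fit a single-centre breast study: a multi-centre coordination committee, gastrointestinal surgeons on the monitoring board, and subcentres. That suggests carried-over text, although the SAP does not say so. This part stands. A reader might infer from 7(3) that the study will be analysed with no controls, and the document as a whole does not support that. The conflicting instruction nevertheless remains in the current text.

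A reader might also infer that surgeon is fully or largely confounded with group, with controls operated on by an unrestricted set of surgeons. The SAP does not support that either. No section says who operates on the controls, and none rules out the same two physicians. The study is in one centre, and 7(2) calls for qualified and largely stable staff. If the same two surgeons do most of the open operations, the imbalance could be small.

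Two further points limit the remedy. The operator is already to be recorded, so no new data item is needed. Restricting controls to two surgeons in the main comparison would change the design, with an accrual cost that the SAP gives no means to estimate: 60 or 80 controls from two surgeons in an enrolment window of November 2024 to June 2025. Covariate adjustment of a binary endpoint with 20 single-port patients could also be fragile if failures are few.

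**Conclusion.** The contradiction is established on the text. Section 7(3) names a comparative population that excludes every planned control and admits a group the design does not contain, and no analysis set elsewhere overrides it. The wording has to be reconciled before analysis. The count of 0 out of 80 (or 60) measures the contradiction and is not an expected outcome.

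The surgeon point holds in a weaker form. On the lenient reading the SAP applies no surgeon restriction to the traditional arm, so imbalance is possible and of unknown size. This rests on the SAP alone. A separate document that states who operates in the traditional arm could settle that part, but it would not remove the conflict within the SAP.

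**What to change.** 1. Rewrite Section 7(3) so that the comparative analysis population is the single-port and traditional breast-conserving surgery groups, in agreement with Sections 3.1, 3.4.1, 3.5, 4.1 and 4.2.
2. Remove the multi-channel reference, or reconcile it with the gap described in Section 1. If a multi-channel comparison is intended, it needs a defined group, intervention and size.
3. State who performs the operations in each arm, and whether the two-surgeon and experience criteria apply to the traditional arm.
4. Use the operator recorded under 7(4): report the main surgical outcomes by surgeon within each arm, and add a sensitivity analysis limited to operations in both arms by the same two surgeons.

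The cost is an edit to one item and a small amount of extra analysis, with no new data collection. The sensitivity analysis will be imprecise: it has at most 20 single-port patients and an unknown number of controls, so it should be presented as a check on the main result. Making it the main comparison would be a change of design and is not asked for here.
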